## 8.5. Criteria for Study Termination

The DMC will review cumulative safety data at regular intervals throughout the study. Should safety signals arise that suggest treatment with CTP-543 poses an unjustified risk to patients, termination of the study or modification of dosing arms may occur upon Sponsor review of the DMC recommendation. The DMC may call for unscheduled data review meetings at any time to ensure appropriate safety monitoring.

Events that could trigger an unscheduled review may include, but are not limited to:

High frequency of dose interruptions

High frequency of, or a trend in, SAEs

High frequency of Grade 3/4 adverse events

Trend in organ system-specific moderate and/or severe adverse events

High frequency of patient discontinuation of treatment due to adverse events

The Sponsor will notify Investigators of any recommendation of study termination by the DMC. The Sponsor will notify Investigators of recommendation for study modification as necessary to protect patient safety including appropriate instructions for removing patients from treatment, while maintaining the blind.

Any termination required by the Sponsor must be implemented by the Investigator, if instructed to do so, in a time frame that is compatible with the patient's well-being. The Sponsor reserves the right to discontinue the study at any time for clinical or administrative reasons.

## 9. DESCRIPTION OF STUDY TREATMENTS

## 9.1. Description of Treatments

Patients will be stratified by extent of scalp hair loss and randomized to CTP-543 or placebo in a 1:2:1 ratio (12mg BID:8 mg BID: placebo).

Treatments arms will include:

- 12 mg CTP-543 every 12 hours
- 8 mg CTP-543 every 12 hours
- Placebo every 12 hours

For each treatment arm, patients will take the first dose of study drug in the clinic on Day 1 of the Treatment Period and will be instructed to take study drug approximately every 12 hours ( $\pm$  3 hours) without regard to food for the duration of the study.

## 9.2. Dose-Adjustment Criteria

No individualized dose adjustment is allowed during the Treatment Period except in the event of intolerability, for which a dose interruption or patient discontinuation may occur at the judgement of the Investigator in consultation with the Medical Monitor (see Section 9.2.1 below for details).

The DMC will review cumulative safety data throughout the study in accordance with the DMC Charter. If the DMC determines that the high dose of CTP-543 should be stopped for safety reasons, patients receiving treatment at that dose will move to the low dose of CTP-543 at the patient's next visit. If an immediate hazard is suspected, patients without an imminent visit may have an Unscheduled Visit for potential dose adjustment to maintain the blind. In the event of CTP-543 treatment arm cessation and dose adjustment to the low dose of CTP-543 treatment, the blind will be maintained and individual patient treatment modifications will not be disclosed.

## 9.2.1. Dose Interruption Safety Criteria and Management

Patients who experience hematologic adverse events as described in Table 3, significant clinical laboratory abnormality, or adverse events that may reflect an unfavorable risk-benefit profile may have their dose interrupted at the discretion of the Investigator. The Medical Monitor(s) should be consulted whenever possible prior to decisions for dose interruption.

Patients who withdraw consent and therefore are discontinued from the study should undergo an Early Termination Visit and subsequent Safety Follow-up Visit as appropriate per Section 8.3.1 Patient Withdrawal Procedures, and associated adverse events followed as described in Section 11 Adverse Events.

Hematology parameters will be assessed bi-weekly for the first 4 weeks of the Treatment Period, and every 4 weeks thereafter for the remainder of the study. Prior to dose interruption, hematology parameters should be confirmed with repeat testing at an Unscheduled Visit within 72 hours, except in severe cases (i.e.: neutrophil counts below 0.5 x 10^9/L) where immediate interruption of dosing is necessary for the safety of the patient. **Blood draws confirming dose interruption criteria should occur prior to the first daily dose on the day of draw.** 

Dose interruption requirements for hematologic abnormalities are provided below. However, less significant changes may warrant clinical intervention and the Investigator should use his/her best clinical judgment when considering a dose interruption whether for singular or aggregate hematology results above the limits provided in Table 3, or for other clinical signs, symptoms, or considerations that suggest dose interruption is in the best interest of the patient.

Table 3: Selected Hematologic Thresholds for Dose Interruption

| Neutrophil Count                             | Dose Adjustment  |
|--|--|
| Between 0.5 to 1 x 10  /L        | Interrupt dose until recovered to greater than 1.5 x 10  /L and  |
| (Grade 3)                                    | resume dosing at previous dose   |
| Less than 0.5 x 10  /L (Grade 4) | Severe case: Interrupt dose immediately and repeat CBC with differential within 72 hours. Recommend hematology consult and contact medical monitor. Permanent discontinuation of treatment should occur upon repeat confirmation of value |
| Female Hemoglobin Level                      | Dose Adjustment  |
| Less than 10 g/dL                            | Interrupt dose until recovered to greater than 10.5 g/dL and resume dosing at previous dose  |
| Male Hemoglobin Level                        | Dose Adjustment  |
| Less than 11.5 g/dL                          | Interrupt dose until recovered to greater than 12 g/dL and resume dosing at previous dose  |
| Platelet Count                               | Dose Adjustment  |
| Less than 75 x 10  /L            | Interrupt dose until recovered to greater than 100 x 10  /L and resume dosing at previous dose   |
| Greater than 750 x 10  /L        | Interrupt dose until recovered to less than 600 x 10  /L and resume dosing as prescribed by the Investigator   |

Upon dose interruption, the parameters that triggered the interruption should be monitored at least weekly until either: 1) recovery above the threshold for dosing resumption is achieved, or 2) a 21-day dose interruption period has elapsed, at which time a discussion between the PI and the Medical Monitor should occur to evaluate whether or not the subject should discontinue treatment permanently. In the case of severe neutropenia (neutrophil counts less than 0.5 x  $10^9/L$ ) patient should interrupt dose **immediately** and repeat CBC with differential within 72 hours. The Medical Monitor should be contacted and a hematology consult should be made if appropriate. Permanent discontinuation of treatment should occur upon repeat confirmation of value. Patients who discontinue treatment due to lack of acceptable recovery of parameters should continue to be followed for all safety and efficacy assessments through the completion of the 24-week treatment period, and will have all endpoints (including efficacy) collected accordingly.

Subjects with both a positive SARS-CoV-2 test (antigen or antibody) AND signs or symptoms consistent with SARS-CoV-2 infection should immediately interrupt dosing with study drug. Dose interruption should continue until symptoms subside (it is not necessary to have a negative SARS-CoV-2 test result). If symptoms do not subside within a 21-day dose interruption period, a discussion between the PI and the Medical Monitor should occur to evaluate whether or not the

subject should discontinue treatment permanently. Signs and symptoms include, but are not limited to: fever or chills, cough, shortness of breath or difficulty breathing, fatigue, muscle or body aches, headache, new loss of taste or smell, sore throat, congestion or runny nose, nausea or vomiting, diarrhea, trouble breathing, persistent pain or pressure in the chest, new confusion, inability to wake or stay awake, bluish lips or face.

Subjects who have signs or symptoms consistent with SARS-CoV-2 infection should be tested for SARS-CoV-2 and do not have to dose interrupt unless the test result is positive. Subjects who have a positive SARS-CoV-2 test (antigen or antibody) but do not have any signs or symptoms consistent with SARS-CoV-2 infection are not required to dose interrupt.

Table 4: SARS-CoV-2 Dose Interruption Criteria

| SARS-CoV-2 Test Result | SARS-CoV-2 Symptoms | Dose Interruption |
|------------------------|---------------------|-------------------|
| Positive               | Yes                 | Yes               |
| Positive               | No                  | No                |
| Negative               | Yes                 | No                |

### 9.2.2. Pharmacokinetic Criteria for Stopping Doses

There are no pharmacokinetic criteria for stopping study drug doses.

## **9.3.** Treatment Compliance

At each scheduled study visit after randomization, the Investigator or designee will interview the patient regarding treatment compliance and compare the number of dispensed versus returned study drug tablets. Patients should strive for 100% compliance with the daily dosing schedule. Retraining on treatment compliance should occur for patients with less than 80% compliance, or greater than 100% compliance, at any visit and the Sponsor should be notified.

## 9.4. Study Drug Materials and Management

Please consult the Pharmacy Manual for a complete description of the study drug and requirements for storage, handling, dispensing, accountability, returns and destruction.

#### 9.4.1. Physical Description of Study Drug

Study drug will include CTP-543 and matching placebo. Details regarding formulation and dosage are presented in Table 5.

**Table 5:** Investigational Product

|               | Investigational Product
(CTP-543 or Placebo) |
|---------------|---|
| Product Name: | CTP-543 or Matching placebo                     |
| Dosage Form:  | Tablet  |

| Dosage Strength of CTP-543 | 8 mg, 12 mg                   |
|----------------------------|-------------------------------|
| Route of Administration    | Oral                          |
| Physical Description       | White, capsule-shaped tablets |

### 9.4.2. Study Drug Packaging, Labeling, and Storage

Study drug will be packaged and labeled by an appropriately qualified vendor. Each patient will receive one 60 count bottle of study medication at each 4-week study visit. Details of the packaging, labeling and dispensing instructions can be found in the Pharmacy Manual.

The label(s) for the investigational product and placebo will include the required caution statements and/or regulatory statements, as applicable per local regulations.

Adequate supplies of study drug will be provided to each site by the sponsor or designee. Study drug should be stored in the original container between 15°C to 25°C (59°F to 77°F), as stated on the product label, in a secure, temperature-monitored, locked area, under the responsibility of the Investigator or other authorized individual until dispensed to the patients.

Study drug dispensed to patients should be stored in the original bottle at room temperature as stated on the package label. No special handling procedures are required. Due to the COVID-19 pandemic, Site to Subject (STS) or Direct to Subject (DTS) shipping services may be warranted in cases where a patient is not able to attend in clinic visits or a site is closed. Additional information can be found in the Pharmacy Manual.

#### 9.4.3. Study Drug Preparation and Administration

No study drug preparation is required. Patients will take the first dose of study drug in the clinic on Day 1 and will be instructed to take study drug approximately every 12 hours for the duration of the Treatment Period. Patients should dose study drug in the clinic on all Study Visit Days after clinical laboratory blood draws are completed.

Study drug should be taken at approximately the same times each day, with water, and without regard to food. Patients should be instructed to take one tablet in the morning and one tablet in the evening, approximately 12 hours apart. If a dose is missed, the patient should skip the missed dose and resume dosing at the next scheduled dose. The patient should not take two doses at the same time. Deviations from prescribed dosing should be discussed at each visit for assessment of compliance and retraining when necessary.

#### 9.4.4. Study Drug Return and Disposal

The Sponsor (or designee) will review with the Investigator and relevant site personnel the process for study treatment return, disposal, and/or destruction, including responsibilities for the site versus the Sponsor (or designee). Specific requirements for destruction or return are defined in the Pharmacy Manual.

### 9.4.5. Study Drug Accountability

To satisfy regulatory requirements regarding drug accountability, all study drug will be reconciled in full. The Investigator or designee must maintain accurate records of the receipt of

study drug, including date received, lot number, amount received, condition of the package, and the disposition of study drug.

Current dispensing records will also be maintained, including the date and amount of medication dispensed to each individual patient. Returned study drug records will be maintained and final study drug reconciliation will also be recorded for each patient.

#### 9.5. Concomitant Medications and Procedures

All medications, including over-the-counter therapies (e.g., vitamins, herbal, and nutritional supplements) and vaccinations (including the SARS-CoV-2 vaccination), taken at the time of the Screening Visit through the Follow-Up Visit will be recorded in the patient's source documentation and documented in the eCRF. Additionally, any prior janus kinase (JAK) inhibitor use or live virus vaccinations (including Herpes Zoster) will be recorded.

To date, there is no clear evidence of any safety concern for receipt of a SARS-CoV-2 vaccine during the treatment period. Existing data on JAK inhibitors and vaccines, including the SARS-CoV-2 vaccine, are insufficient to conclude whether JAK inhibitors, including CTP-543, have an effect on vaccine effectiveness, though data to date do not suggest that a major effect is likely. Subjects considering enrollment in this CP543.3002 trial may wish to receive their vaccine(s) before entering the trial. As subject and public health are paramount, SARS-CoV-2 vaccination should not be delayed or withheld for subjects already enrolled in the CTP-543 trial.

Knowledge about the vaccines and virus is continually growing. The Sponsor will notify sites as new information is obtained that might further inform vaccine-related questions during the study. Please also carefully read the product information (package insert) for the vaccine being used, noting any specific precautions or warnings for concomitant administration with JAK inhibitors or immunosuppressants.

Any concomitant medication deemed necessary for the wellbeing of the patient may be given at the discretion of the Investigator. Use of medications that are prohibited per protocol will require patient withdrawal from the study. However, under certain circumstances, and in consultation with the Medical Monitor, short-term use of a prohibited medication may not necessitate withdrawal when its use is unlikely to unfavorably alter the risk-benefit of subject participation or confound the study endpoints.

The following treatments are not permitted during the study:

- Medications that may affect hair regrowth or immune response (such as: corticosteroids administered orally, by injection, or applied to areas of skin affected by alopecia; platelet-rich injections; topical application to affected areas of anthralin, squaric acid, diphenylcyclopropenone, or minoxidil;
- Chronic or long-term treatment with systemic immunosuppressive medications including but not limited to methotrexate, cyclosporine, and azathioprine; chloroquine derivatives; Janus kinase inhibitors (ruxolitinib, tofacitinib, etc), etanercept; or biologics (adalimumab, atlizumab, canakinumab, certolizumab, fontolizumab, golimumab, infliximab, mepolizumab, rituximab, secukinumab, tocilizumab, ustekinumab);

- NOTE: a short course of steroid treatment for acute treatment of a condition during the trial may be allowed following discussion with the Medical Monitor
- Use of strong CYP3A4 inhibitors (such as, but not limited to clarithromycin, conivaptan, grapefruit juice, indinavir, itraconazole, ketoconazole, lopinavir/ritonavir, mibefradil, nefazodone, nelfinavir, posaconazole, saquinavir, telaprevir, telithromycin, voriconazole, or fluconazole) dosed for systemic exposure;
- Use of strong CYP3A4 inducers (such as, but not limited to barbiturates, carbamazepine, efavirenz, glucocorticoids, modafinil, nevirapine, oxcarbazepine, phenobarbital, phenytoin, pioglitazone, rifabutin, rifampin, St. John's Wort, or troglitazone) dosed for systemic exposure.
- Live vaccines including, but are not limited to) the measles, mumps, and rubella (MMR) vaccine; intranasal flu vaccine; and Zostavax (but not Shingrix) for herpes zoster.

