Patient safety will be monitored throughout the trial by the Investigator and supported by regular review by the Medical Monitor and DMC. Chemistry and hematology laboratory values will be assessed under fasted conditions bi-weekly for the first month of the treatment period, followed by every 4 weeks through the remainder of the study. Lipid levels will be assessed every 4 weeks throughout the Treatment Period. In light of the COVID-19 pandemic, challenges in the conduct of study visits may arise from quarantines, site closures, and/or travel limitations. To ensure the safety of trial participants and to minimize risk to trial integrity, alternative methods for drug dispensation and assessments, including telemedicine visits and clinical laboratory blood draws at a local laboratory or via a Home Health Care agency, may be offered for those trial participants who may no longer have access to the investigational site. Significant cytopenias or other hematologic abnormalities will be managed by severity through dose interruption or discontinuation, and signs and symptoms of infection will be closely monitored and treated promptly. Patients who experience intolerable symptoms during treatment may discontinue treatment at the judgement of the Investigator, but will be followed for safety and efficacy assessments until Week 24, unless they withdraw consent. Patients may withdraw consent at any time.

Following the 24-week Treatment Period, patients will have the opportunity to continue receiving treatment in an Open-Label Extension study. If a patient does not wish to continue into the Open-label

Extension study, they will complete treatment at Week 24 and return in 4 weeks for the Post-Treatment Safety Follow-up to assess safety following treatment completion.

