Lipid levels will be assessed every 4 weeks throughout the Treatment Period. In light of the COVID-19 pandemic, challenges in the conduct of study visits may arise from quarantines, site closures, and/or travel limitations. To ensure the safety of trial participants and to minimize risk to trial integrity, alternative methods for drug dispensation and assessments, including telemedicine visits and clinical laboratory blood draws at a local laboratory or via a Home Health Care agency, may be offered for those trial participants who may no longer have access to the investigational site. Additional information will be documented in study manuals. Significant cytopenias or other hematologic abnormalities will be managed by severity through dose interruption or discontinuation, and signs and symptoms of infection will be closely monitored and treated promptly. Patients who experience intolerable symptoms during treatment may discontinue treatment at the judgement of the Investigator, but will continue in the study and complete all assessments unless they withdraw consent. Patients may withdraw consent at any time.

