## 8.3. Patient Withdrawal Criteria

For all patients, it is the intent that patients who discontinue study medication (at any time) for any reason will continue to be followed for all protocol-planned study visits through the completion of the 24-week treatment period, and will have all endpoints (including efficacy) collected accordingly.

The Investigator, Sponsor, or its designee may decide a patient should discontinue treatment at any time and for any reason. In addition, patients will discontinue randomized treatment if they:

- Experience an intolerable adverse event: such events include, but are not limited to, adverse events ≥ Grade 4\*, bone marrow-related events, a ≥ Grade 3\* cardiac event (\*CTCAE v5.0 criteria);
- Require a medication that is prohibited by the protocol. However, under certain circumstances, and in consultation with the Medical Monitor, short-term use of a prohibited medication may not necessitate withdrawal of treatment when its use is unlikely to unfavorably alter the risk-benefit of subject participation;
- In the opinion of the Investigator, have any medically appropriate reason;
- Become pregnant;
- Have a serious adverse event associated with a SARS-CoV-2 infection;
- The Investigator believes that further treatment is undesirable or the risk-benefit profile has become unfavorable.

Furthermore, dose interruptions lasting more than 21 days may require treatment discontinuation on a case by case basis following consultation with the Medical Monitor.

In addition, patients are free to withdraw from participation in the study at any time, for any reason, and without prejudice. The Investigator must withdraw any patient from the study if the patient withdraws consent and requests to stop participating in the study. Patients who withdraw or are withdrawn from the study will not be replaced.

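### Protocol 9.5 removes patients from the study for prohibited medication, whereas 8.3 only stops their treatment; following 9.5 loses Week 24 SALT and SPRO

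*Protocol*

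**What the plan says.** Protocol 9.5 gives the rule "Use of medications that are prohibited per protocol will require patient withdrawal from the study". It allows an exception, in consultation with the Medical Monitor, for short-term use, which "may not necessitate withdrawal when its use is unlikely to unfavorably alter the risk-benefit of subject participation or confound the study endpoints".

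Protocol 8.3 opens with the intent that "patients who discontinue study medication (at any time) for any reason will continue to be followed for all protocol-planned study visits" to the end of the 24-week period, with all endpoints collected, efficacy included. It then lists reasons to discontinue randomized treatment, one of which is "Require a medication that is prohibited by the protocol". Its own exception is that short-term use "may not necessitate withdrawal of treatment when its use is unlikely to unfavorably alter the risk-benefit of subject participation". In 8.3 the Investigator must remove a patient from the study only when the patient withdraws consent and asks to stop.

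Three other places keep patients who stop drug in follow-up, though for other triggers:

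- Synopsis, Methodology (intolerable symptoms): "but will be followed for safety and efficacy assessments until Week 24, unless they withdraw consent".
- Protocol 7.1 (intolerable symptoms): "but will continue in the study and complete all assessments unless they withdraw consent".
- Protocol 9.2.1 (blood counts that do not recover): such patients "should continue to be followed for all safety and efficacy assessments through the completion of the 24-week treatment period".

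Protocol 12.4.2 applies a treatment-policy strategy to discontinuation of study treatment. SAP 8.2.1 keeps SALT scores after treatment stops for patients still on study, and imputes missing scores under MAR, separately by arm. SAP section 13 does not mention the conflict.

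**The concern.** Two current sections give different instructions for the same patient. Under 8.3 the patient stops study drug and still attends Week 24. Under 9.5 the patient leaves the study and has no scheduled Week 24 visit.

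The exceptions differ as well. Section 8.3 judges short-term use on risk-benefit alone, while 9.5 adds a test of confounding the endpoints. Short-term use of an agent that may affect hair could therefore be exempt under 8.3 and still mean leaving the study under 9.5.

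What is lost is the outcome the strategy asks for: response at Week 24 after stopping drug, perhaps while taking something else that acts on hair. The replacement is a model-based value drawn from the patient's own arm, although this patient's later course may differ from that of patients who stayed. The first key secondary endpoint, SPRO at Week 24, is affected in the same way (SAP 8.3.1).

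**Working it through.** **1. The plan's own figure.** Protocol 12.1 assumes 40%, 26% and 9% response (12 mg, 8 mg, placebo), with 110, 220 and 110 patients and two-sided alpha 0.025 (z = 2.241). Using power = Φ[(d − c − z·se0)/se1], with continuity correction c = 0.5(1/n1 + 1/n2), se0 pooled and se1 unpooled:

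- 8 mg: d = 0.17, c = 0.0068, se0 = 0.0470, se1 = 0.0402, giving 92.5% (stated: about 92%).
- 12 mg: d = 0.31, c = 0.0091, se0 = 0.0580, se1 = 0.0541, giving 99.9% (stated: above 99%).

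The stated power reproduces. The conflict does not depend on it.

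**2. Can an Early Termination visit replace Week 24?** Section 9.2.1 names that visit for patients who withdraw consent. By SAP 8.1.2 and SAP Table 2, an early-termination assessment counts as Week 24 for efficacy only on Days 166–172. The earlier SALT windows are Days 26–32, 54–60, 82–88, 110–116 and 138–144.

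- SALT: 5 × 7 = 35 of the 164 days from Day 2 to Day 165, or 21%.
- SPRO (Weeks 12, 16 and 20 only): 3 × 7 = 21 of 164, or 13%.

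A score inside one of these windows can at most inform the imputation. A score outside every window is not assigned to a visit. This is a count of days; actual visits may cluster on scheduled days.

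**3. How the missing SALT is handled.** The primary analysis imputes it under MAR within arm. Sensitivity 1 (SAP 8.2.3) imputes from placebo only if a treatment-emergent adverse event or lack of efficacy is recorded as the reason; otherwise it again uses the patient's own arm. The tipping-point analysis (Sensitivity 2) adjusts all imputed values.

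**4. Possible bias in the risk difference.** One patient can move it by at most 1/110 = 0.91 points (12 mg or placebo) or 1/220 = 0.45 points (8 mg).

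Assume imputation near the planned arm rate, which fits patients with little post-baseline SALT. Assume also that true response lies between 9% (off drug) and 60% (another effective agent). The shift per patient is (imputed − true)/n, with the sign reversed for placebo. For a withdrawn fraction f of one arm it is f × (imputed − true); f = 2–5% is assumed.

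| Arm with withdrawals | True 9%: per patient | f = 2–5% | True 60%: per patient | f = 2–5% |
|---|---|---|---|---|
| 12 mg | (0.40 − 0.09)/110 = +0.28 | +0.62 to +1.55 | (0.40 − 0.60)/110 = −0.18 | −0.40 to −1.00 |
| 8 mg | (0.26 − 0.09)/220 = +0.08 | +0.34 to +0.85 | (0.26 − 0.60)/220 = −0.15 | −0.68 to −1.70 |
| Placebo | 0 | 0 | (0.60 − 0.09)/110 = +0.46 | +1.02 to +2.55 |

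Entries are percentage points of active minus placebo; a plus sign favours active.

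**5. What would overturn significance?** This is an unstratified comparison at the planned rates, against z = 2.241.

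- 8 mg: 57/220 versus 10/110 gives z = 3.58 (pooled) or 4.17 (unpooled). Significance is first lost at 40/220 (17 fewer, pooled z = 2.17) or 38/220 (19 fewer, unpooled z = 2.19). That is 17/220 to 19/220, or 8–9% of the arm.
- 12 mg: 44/110 versus 10/110. Significance is first lost at 21/110 (23 fewer, z = 2.13 to 2.15), or 23/110 = 21% of the arm.

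**The case against.** The strongest case is that this is a wording slip with little consequence.

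- **Section 9.5 is not alone in ordering study withdrawal.** Protocol 8.4 does so after emergency unblinding. That is true, but it is a different event with no competing rule. It is also true that, of the sections that keep patients in follow-up, only 8.3 addresses prohibited medication.
- **Few patients may be affected.** A note in 9.5 allows a short steroid course for an acute condition after discussion with the Medical Monitor, and both exceptions are discretionary. This narrows the group but leaves the rule for everyone else.
- **Section 8.3 speaks of needing a prohibited drug, 9.5 of using one.** A patient who needs and takes it meets both. Use without need falls only under 9.5, which points to leaving the study.
- **The strategy in 12.4.2 names treatment discontinuation, not use of another agent, and describes the primary analysis.** This stands as a description. But 8.3 makes the event a treatment stop, which brings it under that strategy, and SAP 8.3.1 analyses SPRO in a similar way to the primary endpoint.
- **The bias ranges are illustrations.** Agreed. The 60% and the 2–5% have no source in the documents, and 60% exceeds the 40% planned for 12 mg. Patients with several earlier SALT scores would be imputed from those scores rather than near the arm average.
- **The plan already limits the risk.** The blinded review of reasons for missing data judged MAR reasonable (SAP 13), and the tipping-point analysis covers all imputed values. Both help with inference, but neither recovers an outcome that could have been observed.

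**Conclusion.** The concern holds. The contradiction between 9.5 and 8.3 is in current text and is certain; its effect on the result is uncertain and probably small. The number of patients and the direction of bias cannot be known from the documents. Under the stated assumptions the largest shift is about 2.6 points, and it arises from placebo patients responding to another agent. At the planned rates and the assumed 2–5%, the primary conclusion is not threatened. The point is worth fixing because it creates avoidable missing data on the primary and first key secondary endpoints and costs almost nothing to correct.

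**What to change.** In Protocol 9.5, replace study withdrawal with discontinuation of study drug, and state that scheduled visits continue through Week 24 unless consent is withdrawn, as in 8.3. Keep the short-term-use exception but word it identically in 8.3 and 9.5. This costs one sentence in 9.5 and matching exception wording in 8.3, with no visits beyond those 8.3 already plans.

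The SAP is dated 2022-06-29 and the synopsis estimated the last visit for June 2022, so follow-up may already be complete. In that case, identify the patients withdrawn under 9.5, by arm and last SALT visit, within the study-discontinuation summary (SAP 6.1) and the missing-pattern summary (SAP 8.2.1). That adds one reason label to output already planned.
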